10.4.8 ADDITIONAL SUB-GROUP ANALYSES

Subgroup analyses will be completed with covariates of sex and age for the primary and secondary endpoints. Lesion location will also be used in a sub-group analysis for primary and secondary outcomes, but it is anticipated that there may not be sufficient variation for this analysis to be completed.

10.4.9 MULTIPLE COMPARISON/MULTIPLICITY

There is only one primary endpoint for which this study is powered. Secondary and exploratory outcomes will provide preliminary information regarding these outcomes in subjects with chronic spinal cord injury undergoing epidural SCS.

10.4.10 TABULATION OF INDIVIDUAL RESPONSE DATA

Data will be tabulated by individual but represented graphically in groups. It is necessary to demonstrate individual differences over time as trajectories.

10.4.11 EXPLORATORY ANALYSES

Exploratory analyses will be performed to begin to understand how epidural stimulation may affect bladder function, bowel function, measures of depression and anxiety, pain, sleep and quality of life. The study is not powered to examine the effect size of any of these outcomes. These outcomes will be used to explore potential relationships through future research.

10.5 SAMPLE SIZE

Subjects will undergo blinded treatment and sham BMAC testing at each monthly appointment during the course of the trial. Assuming nonattendance to be approximately 25%, we expect subjects to complete at least 9 sessions. With a power of 0.95 and alpha of 0.025 for a two level ANOVA, we assume a correlation among repeat measure of 0.5. By assuming a baseline mean magnitude of 0.3 and a clinically significant change of 0.2 while assuming a within group standard deviation of 0.25 (resulting in an effect size of 0.4), we estimate that we will need at least 56 subjects to demonstrate significance for the primary outcome.

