4 STUDY DESIGN AND ENDPOINTS

4.1 DESCRIPTION OF THE STUDY DESIGN

This is a quasi-experimental study of chronic spinal cord injury patients using same-subject preoperative and sham controls to determine primary and secondary outcomes. Testing of sham vs. stimulation phases during visits will be randomized and double blinded.

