10.4 DESCRIPTION OF STATISTICAL METHODS

10.4.1 GENERAL APPROACH

This study represents a single-arm quasi-experimental, multiple, sham-controlled crossover study. This design is possible because of the rapid onset and offset of the effect of epidural stimulation as previously reported. This protocol provides the opportunity to test outcome measures intensely in each individual subject over different stimulation settings with sham control longitudinally. The intention of the longitudinal assessments is to search for improvements over time with increased understanding of the stimulation parameter space. As such most outcomes utilize the repeated measures ANOVA.

Baseline data relevant to spinal cord injury movement and its adverse effects will be measured in the hopes of providing guidance for future generalizability. Descriptive statistics will be reported as means with standard deviations. Tests will be considered statistically significant when alpha is less than 0.05 for two-tailed tests. All assumptions for statistical tests will be evaluated before use of the test and corrected if necessary and possible.

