10.4.2 ANALYSIS OF THE PRIMARY EFFICACY ENDPOINT(S)

The primary outcome is volitional movement as measured by the brain motor control assessment (BMCA). The BMCA uses surface electromyography (sEMG) to track changes in muscle amplitudes relative to a population control in a normalized fashion. In this protocol, the lower extremity BMCA is used to track progress during the trial and is reported as a vector, which consists of the magnitude of the response vector (RV) and the similarity index (SI). The response vector is composed of the magnitudes of the sEMG where each dimension is an included muscle. The similarity index is the inner product of the normalized response vector in controls for a single maneuver with the normalized RV from the subject for that maneuver. The RV is reported in microvolts while the SI is reported as a value between 0 and 1, both continuous variables. As a pair, these are referred to as the voluntary response index (VRI).

The VRI for each maneuver will be averaged over all of the muscle groups at each appointment, resulting in a single sham vector and a single stimulation vector for each regularly scheduled appointment. By design, subjects undergoing the protocol should have response magnitudes and SI of 0 as baseline readings. By normalizing the VRI to (200, 1), it is possible to report a clinically significant change. For example, computing the normalized magnitude for a response magnitude of 50 uV and a SI of 0.2 would result in $\sqrt{(50/200)^2 + (0.2/1)^2} = 0.32$. Based on the limited data using this particular outcome, we feel a clinically significant change would be a distance of 0.2. This allows muscles groups to coordinate or improve in magnitude.

The primary outcome is whether subjects regain volitional movement during epidural stimulation. The hypothesis is then that the VRI should be higher during blinded treatment when compared to sham stimulation. While the time-course of change and measurements of plasticity are also interesting, the very small amount of pre-existing preliminary data available encourages efforts to focus on major changes in the primary outcome. For each subject,

we assume subjects will be able to attend at least 10 appointments, and, therefore, undergo 10 BMAC tests, resulting in 10 VRIs during treatment and sham.

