The repeated measures ANOVA will be used to compare sham and treatment where alpha is assumed to be 0.025 (two tailed) and power 0.95. The correlation between repeated measures is assumed to be 0.5. The ANOVA residuals will be assessed for normality and the groups will be assessed for homoscedasticity. If there are significant violations of these assumptions then Friedman's test will be used instead. The data will be displayed with means and 95% confidence intervals between treatment and sham for each subject and as a group over time.

Missing data will be analyzed to examine for randomness of omission. If the missing data is determined to be reasonably random, then predictive mean matching will be used for imputation. The distribution of the complete data set will be examined with and without the imputed data.

Data from subjects with incomplete data from dropout will be included in the final analysis unless the subject requested removal of their data. Incomplete data will be pooled per session.

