10.4.6 BASELINE DESCRIPTIVE STATISTICS

Baseline characteristics will be described including demographics, medical history, and all baseline assessments of this single-arm study.

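### The 56 subjects in section 10.5 match a calculation for two independent groups, but the primary test compares sham and stimulation within each subject

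*Combined protocol and SAP*

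**What the plan says.** Section 10.5 (Sample Size) sets the error rates and the correlation: "With a power of 0.95 and alpha of 0.025 for a two level ANOVA, we assume a correlation among repeat measure of 0.5". It expects at least nine completed sessions, takes a baseline mean magnitude of 0.3 and a clinically significant change of 0.2, and concludes with a "within group standard deviation of 0.25 (resulting in an effect size of 0.4), we estimate that we will need at least 56 subjects".

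Section 10.4.2 describes the primary test in matching terms: "The repeated measures ANOVA will be used to compare sham and treatment where alpha is assumed to be 0.025 (two tailed) and power 0.95". It adds that "The correlation between repeated measures is assumed to be 0.5", without saying which measures are correlated.

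The design is a same-subject comparison throughout. Section 4.1 describes a study "using same-subject preoperative and sham controls to determine primary and secondary outcomes". Section 10.4.1 says "This study represents a single-arm quasi-experimental, multiple, sham-controlled crossover study", and section 10.4.6 refers to "all baseline assessments of this single-arm study". Under section 10.4.2 the averaging is done for each subject, "resulting in a single sham vector and a single stimulation vector for each regularly scheduled appointment". Section 10.6.1 confines randomization to the sham-controlled testing within clinic appointments. No section describes separate groups of sham and stimulation subjects.

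**The concern.** A sample size should be calculated for the contrast that will be tested. Here that is the mean stimulation-minus-sham difference within a subject, and its precision depends on the SD of that difference. Section 10.5 gives only a within-group SD and one undefined correlation.

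The meaning of the correlation matters because the two possible readings act in opposite directions. A correlation of 0.5 between sessions makes averaging over sessions less effective and so increases the variance of a subject's mean. A correlation of 0.5 between sham and stimulation reduces the variance of their difference.

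The figure of 56 is the only justification the plan gives for how many people undergo laminectomy and device implantation, and section 10.4.9 says the primary endpoint is the only one the study is powered for. If the figure comes from another design, the plan does not state the power of its own primary comparison.

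**Working it through.** **Inputs.** From section 10.5: difference 0.2, SD 0.25, effect size 0.4, at least 9 sessions, correlation 0.5, alpha 0.025, power 0.95. Section 10.4.2 makes the alpha two-tailed. The stated effect size is Cohen's f for two levels: f = (0.2/2)/0.25 = 0.4.

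**Reproducing the 56.** For a repeated-measures ANOVA with a between-groups factor (two independent groups, m measurements per subject, correlation ρ between measurements), the F test has 1 and N − 2 degrees of freedom and noncentrality

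λ = f² × N × m / (1 + (m − 1)ρ).

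With f = 0.4, m = 9 and ρ = 0.5, λ = 0.16 × N × 9/5 = 0.288N, which is 16.13 at N = 56. Power at alpha 0.025:

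| N | Power |
|---|---|
| 54 | 0.9458 |
| 55 | 0.9498 |
| 56 | 0.9535 |

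The smallest N that reaches 0.95 is 56, or 28 per group. With equal groups, 56 is also the answer for m = 8, 10 and 11 (power 0.9511, 0.9554 and 0.9569); m = 7 gives 58 and m = 12 gives 54.

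**The planned comparison.** For a within-subject contrast the F test has 1 and N − 1 degrees of freedom and λ = N × (0.2/SD_d)², where SD_d is the SD of a subject's stimulation-minus-sham difference (or mean difference). The plan does not fix SD_d, so four readings of its inputs were tried:

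- A. One pair, sham-stimulation correlation 0.5: SD_d = 0.25 × √(2 × (1 − 0.5)) = 0.250.
- B. Nine sessions averaged, between-session correlation 0.5, conditions uncorrelated: SD_d = 0.25 × √(2 × (1 + 8 × 0.5)/9) = 0.264.
- C. One pair, conditions uncorrelated: SD_d = 0.25 × √2 = 0.354.
- D. Nine sessions averaged, correlation 0.5 between all measurements: SD_d = 0.25 × √(2 × 0.5/9) = 0.083.

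| Reading | SD_d | Power at N − 1 | Smallest N for 0.95 | Power at that N | Power at 56 |
|---|---|---|---|---|---|
| A | 0.250 | 0.9482 | 27 | 0.9563 | 0.9998 |
| B | 0.264 | 0.9434 | 29 | 0.9514 | 0.9995 |
| C | 0.354 | 0.9467 | 50 | 0.9510 | 0.971 |
| D | 0.083 | 0.9054 | 6 | 0.9771 | above 0.9999 |

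None gives 56. These N values show the mismatch; they are not proposed as replacements.

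**What would make 56 right.** Power at N = 56 falls to 0.95 when SD_d = 0.376. With an SD of 0.25 per condition and one pair, that requires a sham-stimulation correlation of 1 − 0.376²/(2 × 0.25²) = −0.13. Otherwise the SD per condition must be larger: 0.376/√2 = 0.266 if the conditions are uncorrelated, or 0.376 if they are correlated 0.5. All of these lie outside the plan's inputs.

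**The case against.** The formula is inferred, since section 10.5 does not name one. The match is also not unique to nine sessions, because 8, 10 and 11 give 56 as well with equal groups. A within-subject calculation with an attrition allowance could land on the same number: reading C with a 10% allowance gives 50/0.9 = 55.6, rounded up to 56. These points stand as limits on saying how the figure was obtained. They do not rescue it. The plan states no such allowance, and its 25% nonattendance is used to set the number of sessions. Whatever formula was used, power 0.95 at 56 does not correspond to the planned contrast on the plan's own inputs.

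The second objection is consequence. The error is conservative, and the plan itself says there is little preliminary evidence (section 10.1), so some margin is reasonable. This is correct, and it is why the point concerns justification and not the validity of the trial.

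The third is that the reassurance depends on 56 being analysed. Section 10.3 limits the analysis set to subjects completing at least 80% of the protocol, while section 10.4.2 keeps data from dropouts, so the analysed number is unclear. In reading C, power would be 0.947 with 49 analysed, 0.926 with 45 and 0.905 with 42; these analysed numbers are illustrative assumptions. The qualification stands.

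**Conclusion.** The concern holds. The figure of 56 with power 0.95 is what a two-independent-group calculation returns, and it does not describe the within-subject test in section 10.4.2. On the plan's inputs that test reaches 0.95 with 6, 27, 29 or 50 subjects, depending on what the 0.5 correlation means and whether sessions are averaged.

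The primary test is not endangered. Power at 56 is at least 0.97 provided that the SD per condition is 0.25, the sham-stimulation correlation is not negative and all 56 subjects are analysed. That the two-group formula was used is an inference from the exact match; that the stated N and power do not fit the planned contrast does not depend on the inference. The correction should be made, but it is a correction to the justification only.

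**What to change.** Rewrite section 10.5 for the within-subject stimulation-minus-sham contrast:

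- Say whether the 0.5 is the correlation between sessions or between sham and stimulation, and state an assumption for the other one.
- State the resulting SD of each subject's mean difference.
- Keep 56, give its power for this contrast, and drop the claim that it is the minimum for 0.95. Say how many of the 56 are expected to be analysed.
- If a sensitivity range goes above a difference SD of about 0.354, label it as assuming either an SD above 0.25 or a negative sham-stimulation correlation.

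Three related inconsistencies can be settled in the same rewrite. Section 10.5 takes a baseline mean of 0.3, while section 10.4.2 expects baseline readings of 0. Section 10.5 uses 9 sessions and section 10.4.2 uses 10. Section 10.4.7.2 plans a formal interim analysis at 60 subjects, which is above 56. The first two do not alter the 56: the baseline mean does not enter f, and with equal groups both session counts give 56.

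The cost is one recalculation and one rewritten paragraph. Neither the number of subjects nor the planned test changes.

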10.6 MEASURES TO MINIMIZE BIAS

10.6.1 ENROLLMENT/ RANDOMIZATION/ MASKING PROCEDURES

Randomization will only occur during sham-controlled testing during clinic appointments. Subjects and the primary testing physician will be blinded to stimulation versus sham in blocked fashion at each appointment. A schedule of assigned programs will be created and recorded by a study coordinator who will deliver stimulation or sham of deidentified sequential program presets at necessary time points at each clinical appointment. In a set amount of stimulation programs delivered during a session, the testing physician and subject will only be able to see these de-identified labels on the programming device and not the properties of the stimulator settings. Due to the significance of previously reported effects, it is very unlikely that subjects will be able to recognize sham and control periods, but blinding is attempted to remove as much bias as possible.

10.6.2 EVALUATION OF SUCCESS OF BLINDING

The subject and testing physician will be given a case report form that will ask whether or not each program had/did not have stimulation.

10.6.3 BREAKING THE STUDY BLIND/PARTICIPANT CODE

Blinding will only be broken during interim and final data analysis.

11 SOURCE DOCUMENTS AND ACCESS TO SOURCE DATA/DOCUMENTS

A Case Report Form will be completed for each subject enrolled into the clinical study. The investigator-sponsor will review, approve and sign/date each completed CRF; the investigator-sponsor's signature serving as attestation of the investigator-sponsor's responsibility for ensuring that all clinical and laboratory data entered on the CRF are complete, accurate and authentic.

Any missing or spurious data will be accompanied by a note to file in the subject's record which will clarify the reason behind it and any action taken afterwards.

Source Data are the clinical findings and observations, laboratory and test data, and other information contained in Source Documents. Source Documents are the original records (and certified copies of original records); including, but not limited to, hospital medical records, physician or office charts, physician or nursing notes, subject diaries or evaluation checklists, pharmacy dispensing records, recorded data from automated instruments, x-rays, etc. When applicable, information recorded on the CRF shall match the Source Data recorded on the Source Documents.

12 QUALITY ASSURANCE AND QUALITY CONTROL

12.1 TRAINING

The principal investigator and co-investigators involved in the study who have surgery roles have completed training to implant epidural spinal cord stimulator. A co-investigator serving as the site investigator, designated for each site, must be the attending surgeon of record for each surgical implantation. Each surgeon has had significant experience implanting SCS paddle electrodes. The investigator-sponsor is responsible for site visit and training the appropriate personnel at each investigational site. The principal investigator will review the method of identifying and enrolling the appropriate subjects into the study.

The principal investigator will provide the necessary documents and forms to assist each investigational site on subject recruitment, procedural follow-up, and the completion of forms for the study.

Each site shall be responsible for assuring uniform data collection and protocol compliance as required by the study protocol and associated documents.

12.2 QUALITY CONTROL COMMITTEE

The Principal Investigator will be responsible for quality control.

13 ETHICS/PROTECTION OF HUMAN SUBJECTS

13.1 ETHICAL STANDARD

The study will be conducted in accordance with the current ICH GCP Guidelines, which are consistent with the ethical principles founded in the Declaration of Helsinki, and in accordance with local applicable laws and

regulations. The IRB/IEC will review all appropriate study documentation to safeguard the rights, safety, and well-being of the subjects. The study will only be conducted at sites where IRB/IEC approval has been obtained. The protocol, sample ICF, advertisements (if applicable), written information given to the subjects, safety updates, annual progress reports, and any revisions to these documents will be provided to the IRB/IEC by the investigator as allowable by local applicable laws and regulations.

13.2 INSTITUTIONAL REVIEW BOARD

This protocol and the informed consent document and any subsequent modifications will be reviewed and approved by the IRB or ethics committee responsible for oversight of the study.

13.3 INFORMED CONSENT PROCESS

13.3.1 CONSENT/ASSENT AND OTHER INFORMATIONAL DOCUMENTS PROVIDED TO PARTICIPANTS

The consent form will include the following:

- Purpose statement
- Participant commitment
- Costs
- Risks
- Benefits
- Disclosure of alternative
- Statement of confidentiality
- Study contact information

When a clinical site investigator and/or research coordinator identifies a candidate for the study, subject eligibility will be confirmed, and the study investigator or coordinator will approach the individual to offer participation. After a thorough discussion to inform the subject and family of the rationale and objectives of the study and the risks, benefits, and alternatives to participation, written informed consent will be obtained from the subject themselves (subject ≥ 18 years of age) or a parent or legal guardian (subject < 18 years of age). Additionally, assent will be obtained for subjects of appropriate age, according to individual institutional practices. If study participation is declined, then all clinical care will be provided to the child in accordance with institutional practice and judgment.

13.4 PARTICIPANT AND DATA CONFIDENTIALITY

All records related to a participant's research will be stored in locked filing cabinets or on computers protected with passwords. The participant's identity on these records will be indicated by a study number rather than by name, and the information linking these study ID numbers with the participant's identity will be kept separate from the research records. The participant will not be identified by name in any publication of the research results.

The collection, transfer and storage of data will be conducted in compliance with the HIPAA Security Rule and structured to minimize risk of PHI disclosure. All recorded data will be entered into a password protected database. All data entry forms will be accessed and completed electronically through a password-protected log-on.

All user interaction with the web-based system, from transmitting access passwords to entering sensitive subject data, is done via 128-bit encryption using the secure HTTPS protocol. Firewalls ensure that only the minimum traffic required for normal operations is allowed to traverse the network of web and database servers. The database production servers will be housed in secure institutional data center facilities and include failover protection designed to minimize potential for server downtime. Minimal required personnel are allowed direct access to production facilities. The study data will remain secure and be maximally protected using production-level data center servers.

13.5 MONITORING

The principal investigator shall select a Monitor(s) qualified by training and experience to monitor the study. A Monitor may be an employee of the principal investigator's organization or an organization contracted by the principal investigator. The Monitor shall assure that the investigators are complying with the signed investigator agreement, the Clinical Investigation Plan/Protocol, IDE regulations and any conditions of approval imposed by the Investigation Site IRB/EC or FDA. Routine monitoring will occur to:

- verify that subject enrollment is being achieved;
- verify that the inclusion/exclusion criteria has been met at enrollment;
- verify that the correct version of the informed consent has been signed by the subject;
- review the medical records of all enrolled subjects to ensure all adverse events have been captured and properly reported;
- verify that the data and imaging are accurate, complete and backed up by source documents;
- verify that all contracts, certifications, and medical licenses for each site are valid through the duration of the study.

14 DATA HANDLING AND RECORD KEEPING

14.1 DATA COLLECTION AND MANAGEMENT RESPONSIBILITIES

Data Management

The principal investigator will monitor each site's data and interpret the respective imaging. The investigator-sponsor will oversee and process data in the following manner:

- Data Management
 - Design and modify data dictionary (the information that is being collected)
 - Design and modify database
 - Quality Control
- Retrieval and Reports

- Assist in preparation of data quality reports
- Assist in preparation of progress reports
- Design and Analysis
 - Consult with biostatistician in design and analysis of research questions

